Phase 1: Optimization of measurement time and software settings of the dry electrode cap EEG in a non-emergency setting in patients in whom a regular EEG is/will be performed for standard medical care.

Phase 2: Optimization of measurement time and software settings of the dry electrode cap EEG in patients close to our target population in a non-emergency setting.

Phase 3: Validation of several existing algorithms and development of one or more new algorithms for LVO-a detection, as well as optimization of logistics and software settings of the dry electrode EEG cap in patients close to our target population in an in-hospital emergency setting.

Phase 4: Validation of several existing algorithms and algorithms developed in phase 3 for LVO-a detection in patients with a suspected AIS in the ambulance, as well as assessment of technical and logistical feasibility of performing EEG with dry electrode caps in patients with a suspected AIS in the ambulance.

STUDY POPULATION

Phase 1: Patients in the outpatient clinic of the Clinical Neurophysiology department of the AMC, in whom a regular EEG has been/will be performed for standard medical care.

Phase 2: Patients with an AIS admitted to the Neurology ward of the coordinating hospital with an LVO-a (after reperfusion therapy).

Phase 3: Patients with a suspected AIS in the emergency room (ER) of the coordinating hospital (before reperfusion therapy).

Phase 4: Patients with a suspected AIS in the ambulance.

INTERVENTION

Performing a dry electrode cap EEG (in phase 1 in the outpatient clinic, in phase 2 during hospital admission, in phase 3 in the ER and in phase 4 in the ambulance).

MAIN END POINTS

- Primary end point: the area under the receiver operating characteristics (ROC) curve of the theta/alpha ratio for diagnosis of LVO-a, based on dry electrode EEG performed by paramedics in the ambulance in suspected AIS patients;
- Secondary end points:

- Sensitivity, specificity, positive predictive value (PPV) and negative predictive value (NPV) of the theta/alpha ratio, and test characteristics of other existing EEG data based algorithms for LVO-a detection (e.g. Weighted Phase Lag Index, delta/alpha ratio);
- Logistical and technical feasibility of paramedics performing dry electrode cap EEG in the ambulance in suspected AIS patients ;

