A triage method for this purpose needs to have both high specificity and high sensitivity for LVO-a. The sensitivity of the diagnostic method is important, because a false negative test result means that the patient would be transported to a non EVT capable hospital, delaying his/her treatment. However, we deem the specificity of the method even more important, for the following reasons. Currently, EVT capable hospitals are overburdened because many patients with a suspected stroke are directly brought to these hospitals, as paramedics often do not want to take the chance of bringing a patient to the 'wrong' hospital. However, only a small part of these patients, circa 7%, is eligible for EVT. This causes EVT capable hospitals to have low capacity for admission of patients that do need specialized care. Additionally, patients with expected stroke currently are first evaluated in the emergency room where they undergo diagnostic procedures, and are then brought to the angiography room to undergo EVT. This takes approximately an hour from entering the hospital to the start of treatment (not all this time is due to diagnostic procedures, but also to other logistical issues that are not addressed in this study). Currently, the angiography room is not being prepared for every patient that is presented to the

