3. STUDY DESIGN

The ELECTRA-STROKE is an investigator-initiated, diagnostic study, that consists of four phases (see below).

STUDY PHASE 1: OPTIMIZING MEASUREMENT TIME, SOFTWARE SETTINGS AND DATA TRANSFER LOGISTICS IN PATIENTS IN WHOM A REGULAR EEG HAS BEEN/WILL BE PERFORMED FOR STANDARD MEDICAL CARE IN A NON-EMERGENCY SETTING

This phase will be carried out in the outpatient clinic of the department of Clinical Neurophysiology of a single center (Amsterdam UMC, location AMC). We will perform dry electrode cap EEGs on patients in whom a regular EEG has been/will be performed for standard medical care. We will compare the regular EEG to the dry electrode cap EEG and this way try to optimize the dry electrode cap EEG measurement, software settings, data transfer logistics and measurement time in a population of patients less vulnerable than our target population, in a non-emergency setting.

STUDY PHASE 2: OPTIMIZING MEASUREMENT TIME, SOFTWARE SETTINGS AND DATA TRANSFER LOGISTICS IN PATIENTS CLOSE TO TARGET POPULATION IN A NON-EMERGENCY SETTING.

This phase will be carried out in the brain care unit of a single center (Amsterdam UMC, location AMC). We will perform dry electrode cap EEGs in a population close to our target population – patients that have been admitted with an AIS and an LVO-a – in a non-emergency setting. We will test technical feasibility of the dry electrode cap EEG in patients that are, in part, unable to cooperate with the procedure (e.g. patients that because of lowered consciousness or agitation will not keep their head still).

STUDY PHASE 3: VALIDATION OF EXISTING ALGORITHMS AND DEVELOPMENT OF NEW ALGORITHM(S) IN PATIENTS IN THE EMERGENCY ROOM

This phase will be carried out in the ER of a single center (Amsterdam University Medical Centers, location AMC). In this phase, we will perform dry electrode cap EEGs in patients that are presented to the ER of the coordinating hospital with a clinically suspected AIS, according to the paramedic that presents the patient, or with a known LVO-a. The last category of patients have undergone an initial work-up in a primary stroke center, where the diagnosis LVO-a has been made, and are transferred to our hospital to undergo EVT. The EEG data of this 'enriched' population, with a higher incidence of LVO-a compared to the primary target population, will be used to validate several existing algorithms and to develop one or more new algorithms for diagnosis of LVO-a.

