STUDY PHASE 4: VALIDATION OF ALGORITHMS IN THE AMBULANCE

This phase is the only multi-center phase of this study. It will be carried out in the ambulances of one ambulance station in Amsterdam and one ambulance station in Alkmaar. These ambulances bring patients with a suspected acute stroke to the following hospitals: AMC, VUMC and OLVG West and Noordwest Ziekenhuisgroep, location Alkmaar. These will therefore be the centers participating in this study phase, as well as the Ambulance Amsterdam. The EEG data will be used to validate several existing algorithms (among which is the Brain Symmetry Index) and the algorithm(s) developed in phase 3. Technical and logistical feasibility of performing ambulant EEGs in patients with a suspected AIS in the ambulance will also be assessed.

Phase 4 will start with a 'run in' phase. The objective of this phase is to assess technical and logistical feasibility of performing ambulant EEGs in patients with a suspected AIS, before commencing inclusion of the prespecified study population. Inclusion will not be consecutive at this stage.

The four phases will not necessarily run consecutively; they may also, in part, run simultaneously. Each phase consists of performing a single dry electrode cap EEG per patient and collecting information on patient characteristics, medical history, medication use, physical and neurological examination performed by the treating physician, imaging studies, diagnosis and treatment as well as logistical and technical information, obtained from the patient, the Emergency Medical Service (EMS) and the treating physician. There are no follow up visits. The study will run until the number of patients required according to the sample size calculation have been included for each phase.

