For study phase 4, where we aim to validate existing algorithms and one or more new algorithms for LVO-a detection, our primary outcome measure is the specificity of the dry electrode cap EEG in a population of patients with a suspected AIS. Sample size calculation is based on an expected specificity of 70% for LVO-a. Originally, sample size calculation was based on an expected LVO-a rate of 7% and a dropout rate of 20%. However, an interim analysis, based on 137 suspected stroke patients in whom an EEG was performed in the ambulance, showed an actual incidence of LVO-a of 5% and a dropout rate of 58%. Patients considered as a 'drop out' had insufficient EEG data quality (n=72), onset of symptoms >24 hours before EEG registration (n=4) or did not give consent for participation in the study (n=3). The EEG data quality increased over the course of the study, so we expect a lower dropout rate for future EEG registrations. Based on these interim data, we adjusted the sample size for phase 4 of the study as follows.

With an incidence of LVO-a of 5% among patients with a clinically suspected AIS in the ambulance, an alpha of 0.05, and a maximum margin of error of 7%, 174 patients with a suspected AIS are required²¹. Assuming a dropout rate of 55%, we intend to recruit 386 patients with a suspected AIS. A patient is considered a 'drop out' if no informed consent is/can be obtained, if no information on the diagnosis made by the treating physician is/can be obtained, or if the EEG measurement is of insufficient technical quality, as judged by the clinical neurophysiologist. Patients included in the 'run in' phase are excluded from the primary analysis and thus not included in our sample size calculation. In the 'run in' phase, we will additionally include 50 patients or less.

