10. STATISTICAL ANALYSIS AND ALGORITHM DEVELOPMENT

STUDY PHASE 1 AND 2

For phase 1 and 2 of this study, the obtained data will not be statistically analyzed, for these phases are meant to gain technical and logistical information on the products being used in a non-emergency setting.

STUDY PHASE 3

For phase 3 of this study, we will determine the diagnostic accuracy of several existing and one or more self-developed EEG data based algorithms for LVO-a detection by comparing the proportions of patients with and without an LVO-a as predicted by EEG to the proportion of patients with and without an LVO-a as diagnosed by the treating physician. A receiver operating characteristic (ROC) curve will be plotted for each algorithm and the optimal cut-off value for each algorithm will be determined. For these cut off values, the sensitivity, specificity, negative predictive value and positive predictive value will be reported with 95% confidence intervals.

ALGORITHM DEVELOPMENT

Data of phase 3 and phase 4 will be used to develop one or more new EEG based algorithms for LVO-detection. We will create artificial intelligence (AI) based algorithm(s). First, we will create a logistic

regression model based on standard EEG features, e.g. time domain characteristics, power spectral density in different frequency bands, coherence measures, and entropy measures. This will be the reference to assess the improvement of the novel AI based models. Second, we will work on EEG classification algorithms based on random forests and support vector machines, using the same EEG features as input. Finally, to support future studies, we will explore new methods that use raw EEG data as input, such as convolutional or recurrent neural networks³³⁻³⁵.

STUDY PHASE 4

For phase 4 of this study, we will determine the diagnostic accuracy of several existing and one or more self-developed EEG data based algorithms for LVO-a detection by comparing the proportions of patients with and without an LVO-a as predicted by EEG to the proportion of patients with and without an LVO-a as diagnosed by the treating physician. An ROC curve will be plotted for each algorithm and the optimal cut-off value will be determined. For this cut off value, the sensitivity, specificity, negative predictive value and positive predictive value will be reported with 95% confidence intervals.

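### Phase 4 picks an undefined optimal cut-off on the same data it is meant to validate; under the Youden or closest-to-corner rule, sensitivity is overstated on average by about 12 to 18 points

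*Combined protocol and SAP*

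**What the plan says.** The Summary describes phase 4 as "Validation of several existing algorithms and algorithms developed in phase 3 for LVO-a detection", and the phase 4 heading in Section 3 also calls it validation.

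Section 10 sets a threshold twice. For phase 3, "the optimal cut-off value for each algorithm will be determined". For phase 4, "An ROC curve will be plotted for each algorithm and the optimal cut-off value will be determined", and the four accuracy measures with 95% confidence intervals follow at that value. Nothing says that the phase 3 value is applied in phase 4, what criterion makes a cut-off optimal, or that selection will be corrected for.

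Other statements bear on this:
- Section 10, algorithm development: "Data of phase 3 and phase 4 will be used to develop one or more new EEG based algorithms for LVO-detection".
- Section 3, on the phases: "they may also, in part, run simultaneously".
- Section 1, on the relative weight of the two error types: "we deem the specificity of the method even more important".
- Section 8.1.2 makes sensitivity, specificity, PPV and NPV of the theta/alpha ratio secondary end points. Section 8.1.1 makes the AUC of that ratio primary.

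**The concern.** A threshold chosen because it performs best in a sample will look better in that sample than in new patients. A validation phase avoids this only if the threshold arrives from outside. Here phase 4 repeats the selection step, so its accuracy figures are apparent performance.

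The effect falls mainly on sensitivity, because there are so few LVO-a cases: with 9, each is worth 1/9 = 11 points. Section 1 explains that a missed LVO-a means transport to a hospital without thrombectomy and a delay in treatment. Overstated sensitivity therefore understates that harm. Phase 4 is also the only ambulance data set, so the study has no later data in which the error would show.

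**Working it through.** **Inputs.** From Section 4.4: expected specificity 70%, margin 7 points, alpha 0.05, LVO-a rate 5%, 174 evaluable in phase 4; about 60 patients with and 240 without LVO-a in phase 3. The documents give no AUC, so it is assumed and varied.

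**1. The plan's own figure.** Section 4.4 states "a maximum margin of error of 7%, 174 patients with a suspected AIS are required". Check: 1.96² × 0.70 × 0.30 / 0.07² = 164.6 patients without LVO-a; 164.6 / 0.95 = 173.3, rounded up to 174. It reproduces. The formula is for a proportion at a cut-off fixed in advance. Expected LVO-a cases: 174 × 0.05 = 8.7.

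**2. Model.** Marker ~ N(0,1) without LVO-a and N(μ,1) with LVO-a, where μ = √2 × Φ⁻¹(AUC); at AUC 0.75, μ = 0.954. The number of cases is Binomial(174, 0.05). The cut-off c either maximises Se + Sp − 1 (Youden) or minimises (1 − Se)² + (1 − Sp)² (closest to corner) in the sample. Reported sensitivity is the observed proportion above c; true sensitivity is 1 − Φ(c − μ), and true specificity is Φ(c). There were 10,000 simulated trials per setting.

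**3. Mean sensitivity, reported / true (difference in points).**

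| AUC | Youden | Closest to corner |
|---|---|---|
| 0.70 | 0.769 / 0.589 (18.0) | 0.720 / 0.577 (14.3) |
| 0.75 | 0.796 / 0.625 (17.1) | 0.755 / 0.615 (14.0) |
| 0.80 | 0.824 / 0.662 (16.2) | 0.789 / 0.656 (13.3) |
| 0.85 | 0.864 / 0.710 (15.4) | 0.831 / 0.700 (13.1) |
| 0.90 | 0.899 / 0.753 (14.6) | 0.873 / 0.746 (12.7) |

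Searching midpoints instead of observed values changes these slightly; the ranges 14 to 18 and 12 to 14 span both. Fixing the counts at 9 and 165 lowers the figures somewhat, to 12.7 (Youden) and 10.8 (corner) at AUC 0.90.

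**4. Other measures at AUC 0.75, Youden (means over trials).** Specificity 0.708 / 0.702; PPV 15.3% / 11.6%; NPV 98.6% / 97.4%. The Wilson 95% interval covers true sensitivity in 89% of trials and true specificity in 95%.

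**5. A useless marker (AUC 0.50).** The reported Youden index averages 0.21 (Youden) or 0.16 (corner) instead of 0.

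**6. Dependence on the rule.** A cut-off at 70% observed specificity, AUC 0.75, gives sensitivity 66.7% reported against 66.0% true. Requiring at least 80% observed sensitivity gives a bias of 8.3 to 9.6 points.

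**7. Frozen cut-off.** Youden on 60/240 phase 3 patients with the same marker distribution, applied unchanged in phase 4 at AUC 0.75: sensitivity 0.673 / 0.673, specificity 0.679 / 0.680, interval coverage 96% and 95%.

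**8. The 7-point margin.** Between 95% and 98% of specificity estimates lie within 7 points of the true specificity at whichever cut-off was selected, so the sample size claim survives in that sense. The selected cut-off itself is unstable: reported specificity has an SD of 16 points (Youden) or 11 (corner) at AUC 0.75.

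**The case against.** The plan names no rule and no AUC, so 12 to 18 points is a conditional average. The documents lean towards specificity: Section 1 ranks it first and Section 4.4 sizes phase 4 on it. A specificity-anchored cut-off would leave less than 1 point of bias. This is correct, and it is why the rule has to be written down. As it stands, the choice can be made after the data are seen. In a single trial the overstatement also varies widely: at AUC 0.75 with Youden, the 10th to 90th percentiles run from about 1 to 35 points.

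The confidence intervals will warn the reader. With 7 of 9 cases detected, the Wilson interval runs from about 45% to 94%, which includes 62%. Coverage of 89% is a modest shortfall, and with exact intervals and 9 fixed cases it is 93% to 96% for AUC 0.60 to 0.90. This softens the consequence, but the point estimate is still shifted upward and a wide interval does not move it back. The NPV change, 1.2 points, is small.

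Only secondary end points are affected. That stands. Section 4.4 calls specificity the primary outcome of phase 4, which differs from Section 8.1.1, but specificity is biased by less than 1 point in any case.

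**Conclusion.** The concern holds and should be fixed. The textual defect is certain: the cut-off is selected and evaluated in the same phase 4 patients, under an undefined criterion and without correction, in a phase presented as validation. Its size depends on the rule and on an assumed equal-variance binormal marker with about 9 LVO-a cases. Under that model, mean overstatement of sensitivity is about 12 to 18 points for Youden or closest-to-corner at AUC 0.70 to 0.90, and close to nil for a fixed-specificity rule. PPV is overstated by 3.7 points at AUC 0.75 with Youden. Specificity and the primary AUC are essentially untouched. These figures cover cut-off selection only; fitting new algorithms on phase 4 data could add optimism that is not quantified here.

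**What to change.** In Section 10, phase 4, state that:
- for the theta/alpha ratio and every other algorithm fixed by then, the cut-off is derived by a named rule (for example Youden, or a stated specificity) from phase 3 dry electrode cap recordings;
- the cut-off is frozen, with a date, before phase 4 EEG values are linked to diagnoses, using the phase 3 data available then if the phases overlap;
- phase 4 sensitivity, specificity, PPV and NPV are reported at that cut-off, and the 7-point margin refers to specificity there;
- any cut-off or algorithm derived with phase 4 data is exploratory, and is reported with cross-validation that repeats cut-off selection, and model fitting where relevant, inside each fold.

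Because Section 4.4 reports an interim look at 137 ambulance patients, the freeze record should also say what was already known about marker values and diagnoses.

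The ordinary bootstrap optimism correction is not enough with so few cases. At AUC 0.75 with Youden it moved mean sensitivity from 0.796 to 0.701 against a true 0.619, while stratified cross-validation gave 0.625 against a true 0.625.

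The cost is wording and a dated record, with no extra patients. The downside is transportability. Phase 3 is an emergency room population "with a higher incidence of LVO-a compared to the primary target population", Section 7.1 gives a subgroup other electrodes, and 60/240 is a planned maximum that Section 4.4 allows to be smaller. If all marker values shifted by 0.25 or 0.5 SD (assumed, AUC 0.75), the Youden index at the frozen cut-off would fall from 0.37 to 0.36 or 0.33. Specificity would move from 68% by 8 to 9 or 15 to 19 points. The results might then look less favourable, but they would be unbiased for the cut-off stated.

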11. ETHICAL CONSIDERATIONS

11.1 REGULATION STATEMENT

This study will be conducted according to the principles of the Declaration of Helsinki (October 2013) and in accordance with the Medical Research Involving Human Subjects Act (WMO).

11.2 RECRUITMENT AND CONSENT

STUDY PHASE 1

For phase 1 of this study, patients will be recruited by the investigators and physicians of the departments of Neurology and Clinical Neurophysiology of the coordinating hospital. Patients fulfilling the in- and exclusion criteria will be given the study information letter and, after having been given time to read, think about and ask questions regarding the content of the letter, will be asked for written informed consent. After informed consent is obtained, the patient will be included in the study.

STUDY PHASE 2

For phase 2 of this study, patients will be screened by the investigators and physicians of the department of Neurology. Patients fulfilling the in- and exclusion criteria of this study, or their legal representative (see chapter 10.3), will be given the study information letter and, after having been giving time to read, think about and ask questions regarding the content of the letter, will be asked for written informed consent. After informed consent is obtained, the patient will be included in the study.

STUDY PHASE 3

For phase 3 of this study, patients will be screened for eligibility in the ER by the investigators. In patients fulfilling the in- and exclusion criteria, an EEG will be performed before obtaining informed consent, and the diagnosis made by the treating physician will be registered. We will withhold any further study procedures until informed consent is obtained. Afterwards, as soon as feasible and preferably within 72 hours after arrival at the hospital or at discharge (whichever comes first), the patient or legal representative (see chapter 10.3) is informed and asked for informed consent by the investigator. If informed consent is granted, we will use the data that have already been obtained and continue the study procedures. If informed consent is not granted, we will ask the patient or legal representative for consent to use the data that have been collected up to that point for this study. If this is granted, we will use the data that have already been obtained but will not proceed with further study procedures. If this is denied, the obtained data will be destroyed. Figure 1 shows the procedure of obtaining deferred consent. If the patient is deceased before informed consent can be asked from the patient or the legal representative, the data that have been collected will be used for the study without having obtained informed consent.

STUDY PHASE 4

For phase 4 of this study, patients will be screened for eligibility in the ambulance by the first responding paramedic. In patients fulfilling the in- and exclusion criteria, an ambulant EEG will be performed before obtaining informed consent, and the diagnosis made by the treating physician will be registered. We will withhold any further study procedures until informed consent is obtained. As soon as feasible and preferably within 72 hours after arrival at the hospital or at discharge (whichever comes first), the patient or legal representative (see chapter 10.3) is informed and asked for informed consent by the investigator. If informed consent is granted, we will use the data that have already been obtained and continue the study procedures. If informed consent is not granted, we will ask the patient or legal

representative for consent to use the data that have been collected up to that point for this study. If this is granted, we will use the data that have already been obtained but do not proceed with further study procedures. If this is denied, the obtained data will be destroyed. Figure 1 shows the procedure of obtaining deferred consent. If the patient is deceased before informed consent can be asked from the patient or the legal representative, the data that have been collected will be used for the study without having obtained informed consent.

ETHICAL CONSIDERATIONS REGARDING DEFERRED CONSENT

Informed consent is fundamental for patient participation in any type of research. However, in acute stroke research, the 'time is brain' principle conflicts with this. For study procedures that need to be performed in the acute setting, asking informed consent in a way that the patient or legal representative has the time to calmly consider the information and ask questions means losing valuable time: an hour delay in initiation of reperfusion therapy (IVT or EVT) in AIS causes a 5-8% decrease in chance of functional independence 3 months after the stroke^{8,9}. Also, asking for informed consent in the acute setting is unlikely to result in a decision that is well thought through, because the patient or legal representative may be overwhelmed and under psychological stress³⁶. Finally, many patients with an AIS are unable to comprehend information regarding study participation due to lowered consciousness, aphasia or anosognosia (not realizing the severity of one's own disease, often due to a lesion of the non-dominant cerebral hemisphere). Only including patients that are capable of giving informed consent would mean selecting a sub group of patients with relatively mild neurological symptoms that is not representative of the population of patients with an LVO-a. A legal representative is often not present in the acute phase³⁷. For the above mentioned reasons, several acute stroke trials have been conducted where informed consent was not required prior to randomization³⁸. According to the Medical Research Human Subjects Act (in Dutch: WMO), for research that can only be conducted in an emergency setting it is allowed to perform study procedures without prior informed consent, if inclusion in the study may benefit the person in urgent need of medical treatment, for as long as the circumstances preventing the giving of consent exist.

Performing an EEG in patients with a suspected AIS in the short time window prior to initiation of treatment is necessary in this study, because the objective is to study the diagnostic accuracy of the ambulant EEG for LVO-a. As soon as the occlusion is being treated (by IVT and/or IAT), this is no longer possible. Although participation in this study does not benefit the patient, it is very important that a

reliable stroke triage method is found for stroke patients in the long term, as described in chapter 1. Considering that EEG is a safe, non-invasive and painless procedure that is used regularly in standard medical practice and does not involve electromagnetic radiation, alongside the above mentioned reasons, we deem it ethical to perform the EEG and register the diagnosis prior to asking informed consent, while withholding all other study procedures until informed consent is obtained. We will ask informed consent as soon as feasible, preferably within 72 hours after arrival at the hospital or at discharge (whichever comes first). If informed consent is not granted, we will ask the patient or legal representative for consent to use the earlier obtained data for this study. If this is granted, we will use the data that have already been obtained but will not proceed with further study procedures. If this is denied, the obtained data will be destroyed. Figure 1 shows the procedure of obtaining deferred consent.

[figure not shown]

Figure 1: Flow chart showing process of obtaining deferred consent for phase 3 and 4 of the study. Acute setting is in the ER for phase 3 and in the ambulance for phase 4.

